Effectiveness and Cost-effectiveness of the Check Your Health Preventive Programme

NCT – 02028195

Approved 21-08-2018

NCT – 02028195

Statistical analysis plan for evaluation of Check your Health Preventive Programme, 2018
Approved 21-08-2018

Statistical Analysis Plan

Check Your Health Preventive Program

Evaluation of a preventive health promotion strategy performed in a primary care and municipality setting

2018

NCT-number: 02028195

Statistical analysis plan for evaluation of Check your Health Preventive Programme, 2018
Approved 21-08-2018

1. Introduction

The Check Your Health Preventive Program (CHPP) was set up to investigate the effectiveness on health outcomes of a preventive health check offered at a population-level to all individuals aged 30-49 years in a large municipality (approximately 26.000 citizens) (1).

Studies have indicated that preventive health checks are likely to reduce CVD risk (2) and to be cost effective (3,4). However, a recent Cochrane review found no reduction in mortality, CVD or cancer in follow-up of preventive health checks (5). Concerns have been raised that the review had significant methodological problems (e.g. weak package of screening tests, primary outcome not appropriate for the diverse set of screening tests) and was mainly based on 20 to 30 years old studies (6). Although, there was no consensus on the effect of preventive health checks e.g. the UK National Health Service Health Check program has been introduced to all citizens aged 40 to 74 years to assess individual disease risk in routine care (7,8).

The objective of the pragmatic household cluster-randomised controlled trial, Check Your Health Preventive Program, was to investigate the effectiveness on health outcomes of preventive health checks at a population level to all individuals aged 30 to 49 years in a primary care setting.

The trial is registered at ClinicalTrials.gov ID: NCT02028195 (7 March 2014).

This is the plan for statistical analysis of the impact of the population-based health check on health outcomes after a 4 years follow-up.

2. Aim

The aim is to evaluate:

Effectiveness of the population-based Check Your Health Preventive Programme conducted in primary care on CVD-risk, physical activity, self-rated health and functional capacity.

3. Outcome measures

Outcome measures are assessed based on information from self-reported questionnaire, from measurements at the health examination and from national registers.

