
Intervention and comparison group will be characterized with respect to baseline demographics. For continuous variables, we report their means and standard deviations (SD), when their distribution is approximately normal, whereas for variables with skewed distributions we report medians and interquartile range (IQR). For categorical variables, we report frequencies and their percentage of the total.

6. Analysis of study outcome measures

For the outcomes, which are only measured for participants in the re-examination (CVD risk, physical activity and self-rated health), we will in addition use a multiple imputation and propensity score based analytic strategy as follows. In the first step, we will use multiple imputation to impute missing values for all who participated in the health checks when randomized to receive it (IG or RG).

Missing data

Frequency and patterns of missing outcome data will be reported with information on reasons (did not receive health check, did not answer question). Missing data are not assumed to be 'missing completely at random', so excluding individuals with missing information will likely introduce selection bias. Multiple imputation will be performed for missing outcomes as described in section 4 by inclusion of baseline characteristics that can explain the missingness. Subsequently, we will treat the missingness mechanism as

at random given the observed information (the Missing At Random (MAR) assumption) and use MICE (12) for multiple imputation and perform analyses after Rubin's rules (13). We will explore the robustness of estimates towards violations of the MAR by conducting sensitivity analyses by, for example, assuming that individuals with an unreported level of physical activity on average have one day less of 30 minutes activity than would have been predicted from their observed covariates. The mimicked analysis based on outcomes available from register-data also allows assessment of the potential violation of the MAR assumption.

Propensity score

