Among all individuals in IG who participated in year 2 examination, we predict the likelihood of participation in the re-examination in year 5. For the participants of the IG in their first health check, we will estimate how their participation in the re-examination depends on their individual characteristics and measurements obtained in the first health check (sex, age, CVD risk, physical activity, etc). This logistic regression will rely on the multiply imputed datasets. Based on the obtained estimates, the propensity for participating in a re-examination is predicted for all in the IG and the CG who participated in the initial health check they were invited to. We will examine the balancing properties of the propensity score obtained, before we use it to weigh the analysis of treatment effect for the various outcomes (CVD risk, physical activity and self-rated health). The model will be developed based on IG and used in CG to perform effect estimation among comparable groups. All analyses will estimate average treatment effects expressed as mean differences for continuous outcomes and absolute risk differences for binary outcomes. We will finally assess the capacity of the propensity score to remove bias in estimated treatment effects by mimicking this analytic strategy for the functional capacity outcomes, and comparing with the estimates obtained for these outcomes when considering the entire invited population.

The treatment effects associated with participation in CHPP will be reported for each outcome measure with 95% confidence intervals. All analyses will account for clustering at household level.

7. Timescale

Analyses plan will be uploaded to clinicaltrials.gov before 15th September 2018.

Preliminary analyses will be performed before 1st April 2019 and final analysis during 2019.

8. Perspectives

The following analyses are planned and will be described separately:

- a) Comparison of health outcomes in CHPP with other municipalities matched on sex, age and educational level.
- b) Cost-effectiveness analysis (direct and total costs, live-years saved, expected life-years gained, GP utilization/hospital admissions)
- c) CHPP effect on CVD and mortality

9. References

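### The register-outcome check of the propensity score and of MAR sets an attender effect against an all-invited effect, and with a non-null effect and little effect in non-attenders the two differ even if the score is perfect

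*SAP*

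**What the plan says.** SAP section 6 confines the imputation and weighting to attenders. It will "impute missing values for all who participated in the health checks when randomized to receive it (IG or RG"); the label RG is not defined, and I read it as the comparison group (CG). Under Propensity score, the propensity for re-attendance is "predicted for all in the IG and the CG who participated in the initial health check they were invited to", and "The model will be developed based on IG and used in CG to perform effect estimation among comparable groups". The same subsection states that "All analyses will estimate average treatment effects expressed as mean differences for continuous outcomes and absolute risk differences for binary outcomes" and that "The treatment effects associated with participation in CHPP will be reported for each outcome measure with 95% confidence intervals".

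To judge whether the score removes bias, the plan relies on "mimicking this analytic strategy for the functional capacity outcomes, and comparing with the estimates obtained for these outcomes when considering the entire invited population". Under Missing data it gives the same exercise a second use: "The mimicked analysis based on outcomes available from register-data also allows assessment of the potential violation of the MAR assumption".

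Section 4 reports 55% attendance in year 1 and expects about the same later. For functional capacity it lists intervention-group (IG) members who attended twice and CG members who attended. It does not list everyone invited. Section 2 puts functional capacity among the effectiveness outcomes: "conducted in primary care on CVD-risk, physical activity, self-rated health and functional capacity".

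**The concern.** Two different effects are being compared. The mimicked analysis estimates an effect in people who came; the benchmark is an effect in everyone invited, of whom about 45% are expected not to come. The plan states no rescaling, no criterion for the comparison, and no expectation that the effect on the register outcomes is null. Section 2 sits uneasily with a null expectation, because it names functional capacity as something the programme may improve.

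This is the only planned step that sets the weighting against a randomised comparison, and it is also offered as evidence on MAR. If the two estimates differ, a reader may blame the score when the cause is dilution. If they agree, a reader may be reassured when a bias has offset the dilution.

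There is also a plain inconsistency. Section 6 describes CVD risk, physical activity and self-rated health as the outcomes seen only in re-examination participants, which implies that functional capacity is not so limited, and it then uses that outcome in everyone invited. Section 4 nevertheless restricts functional capacity to attenders.

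**Working it through.** The plan gives no figure for this check, so there is nothing of its own to reproduce.

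**Inputs from the SAP (section 4).** Attendance a = 0.55, with 0.45 to 0.65 as my range; 10,505 people in the two groups, taken as 10,505/2 = 5,252.5 per group.

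**Assumed inputs.** SD of work participation 0.35 of full time; 30% (or 45%) of the IG attending twice; an illustrative first-attender effect D = 0.02 of full time.

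**1. Size of the mismatch.** Let r be the effect of invitation in non-attenders as a fraction of D. The all-invited effect is

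B = aD + (1 − a)rD, so D/B = 1/[a + (1 − a)r].

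| a | r | D/B |
|---|---|---|
| 0.55 | 0 | 1/0.55 = 1.82 |
| 0.65 | 0 | 1/0.65 = 1.54 |
| 0.45 | 0 | 1/0.45 = 2.22 |
| 0.55 | 0.25 | 1/0.6625 = 1.51 |
| 0.55 | 0.5 | 1/0.775 = 1.29 |
| 0.55 | 1 | 1.0 |

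The ratio applies to mean differences and to risk differences.

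**2. What the raw comparison then shows.** With r = 0, an unbiased mimic exceeds the benchmark by (1 − a)D = 0.45D. At D = 0.02 the benchmark is 0.55 × 0.02 = 0.011 and the gap is 0.009. A mimic biased by −0.009 would agree exactly. At D = 0 the gap is zero and raw agreement is the right yardstick.

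**3. Simulation.** Settings: 5,252 per group, 55% attending, 30% attending twice, outcome-health correlation 0.5, log-odds per SD of health 0.3 for attendance and 0.5 for re-attendance, a correct re-attendance model, r = 0, 1,500 runs per scenario. The rescaled gap is the mimic minus benchmark/a.

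| Scenario | Raw gap | Rescaled gap |
|---|---|---|
| D = 0.02, stable health, first-attender weights | +0.0092 | 0.0000 |
| D = 0.02, year 2 to year 5 health correlation 0.8, first-attender weights | +0.0045 | −0.0046 |
| Same, twice-attender weights | −0.0030 | −0.0120 |
| D = 0, health correlation 0.8, first-attender weights | −0.0047 | – |
| D = 0, health correlation 0.8, twice-attender weights | −0.0120 | – |

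With an effect present, the rescaled gap recovers the bias and the raw gap does not. With no effect, the raw gap recovers it.

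**4. Twice-attender target.** Let s = 0.30 attend twice with effect 0.02, and let those attending once have effect E1. Then B = 0.30 × 0.02 + 0.25 × E1. If E1 = 0.02, B/0.55 = 0.020 and the division matches. If E1 = 0, B/0.55 = 0.006/0.55 = 0.0109, and an unbiased mimic of 0.02 leaves a gap of 0.0091. For this target the division is not a general remedy.

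**5. Precision.** Ignoring weighting and clustering, the mimic compares 0.30 × 5,252.5 = 1,576 with 0.55 × 5,252.5 = 2,889 people. Its variance is V_M = 0.35²(1/1,576 + 1/2,889), a standard error of 0.0110. The benchmark has V_B = 0.35² × 2/5,252.5, a standard error of 0.0068. The attenders are a subset of those invited, so the covariance is about V_B.

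- Raw gap: 1.96√(V_M − V_B) = 0.017 (simulation 0.0164).
- Rescaled gap: 1.96√(V_M + V_B/a² − 2V_B/a) = 0.020 (simulation 0.0200).

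If 45% attend twice, the simulated half-widths are 0.0131 and 0.0172. Dilution alone exceeds the raw half-width when 0.45D > 0.0164, that is D > 0.036 (0.0131/0.45 = 0.029 if 45% attend twice).

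**The case against.** The strongest reply is that the defect would seldom be visible. Every illustrated gap lies inside its own 95% half-width, before and after rescaling, and an effect of 0.036 of full time is about 1.9 weeks of a 52-week year. The plan gives no effect size suggesting that much. This stands, and it limits the weight of the point.

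Three further replies also stand in part. First, the plan speaks of a comparison and ties no decision to agreement; but it offers no other yardstick for the score's capacity to remove bias. Second, section 4 points towards a twice-attender target, for which step 4 shows that simple division may not match. Third, section 3.4 measures work participation and sick leave before the invitation date without saying which IG invitation. Year 5 is the natural reading for an effectiveness outcome. If year 2 were meant, the effect would be null by design and raw agreement would be the right yardstick.

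A reader might infer that agreement is a valid test only when the effect is near zero, without further condition. That goes too far: it needs little or no effect in non-attenders, which the SAP neither states nor excludes, and if non-attenders had the same effect the ratio would be 1.0. A reader might also infer that the check will show bias with the wrong sign. That depends on assumed values: a bias of −0.005 is reversed only if D exceeds about 0.005/0.45 = 0.011.

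**Conclusion.** The mismatch is real but its reach is limited. As written, the check compares effects in two populations. If invitation has little or no effect in non-attenders and the true effect is not zero, they differ under a perfect score by a factor of 1.82 at 55% attendance (1.54 to 2.22 over 65% to 45%; 1.29 if non-attenders have half the effect). Disagreement can then reflect dilution, and agreement can mask bias.

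The factor rests on the SAP's attendance figure and on the assumption about non-attenders. The precision figures rest on the assumed SD of 0.35 and the assumed share attending twice. The documents do not support concluding that the planned estimates for CVD risk, physical activity or self-rated health are wrong because of this: the check feeds into none of them, and balance checks and a separate MAR sensitivity analysis are also planned.

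Scaling the benchmark is a change to consider. The contradiction between section 4 and section 6 on the functional-capacity population does not depend on any of these assumptions and should be fixed in any case.

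**What to change.** 1. In section 4, list the all-invited randomised population as an analysis population for the register-based functional-capacity outcomes, so that it agrees with section 6. In section 3.4, state which invitation date anchors these outcomes in the IG.

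2. In section 6, state which population the weights target.
   - For first attenders: compare the mimic with the all-invited estimate divided by IG year-2 attendance, state the assumption that invitation has no effect in non-attenders (including through attending household members), and report the difference with a household-clustered 95% confidence interval.
   - For twice-attenders: run a first-attender version of the check as well, or state that the division does not give the matching benchmark and that a gap may reflect dilution.

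The cost is SAP wording and a little extra register analysis, with no new data. The interval for the comparison widens from about 0.016 to 0.020 on the assumed SD (0.013 to 0.017 if 45% attend twice). An assumed within-household correlation of 0.2 in two-person households takes the rescaled figure to about 0.021 (0.018). Rescaling corrects the target of the comparison but does not make it more precise.

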3.4. Functional capacity

Functional Capacity (sick leave, working status), affiliation to the labour market (work participation in the last year) will be assessed based on the national register of social transfer payments (DREAM).

Work participation will be described as a fraction of full-time employment in the 52 weeks before the invitation date and analysed as a continuous measure.

Sick leave will be measured as a dichotomous variable and as categories of number of sick-leave periods over 3 weeks during the last year before invitation date.

4. Analysis Population

[figure not shown]

Figure 1. Participants in Check your Health Preventive Programme, Randers

NCT-number: 02028195

Statistical analysis plan for evaluation of Check your Health Preventive Programme, 2018

Approved 21-08-2018

All citizens aged 30-49 years in the municipality of Randers on January 1, 2012 were randomized into five groups (n=26,216) (Figure 1).

The trial was performed as a pragmatic household-cluster randomized controlled trial and included 10,505 individuals. The Intervention group (IG) was defined as the population invited to attend the health check in year 2 and re-invited in year 5, whereas the comparison group (CG) was defined as the population invited to attend in year 5.

A total of 55% of the invited population participated in the health check in year 1, 2012-2013 (11). We expect a similar proportion of the population will participate in the following years.

The actual study population will differ according to the different outcome measures:

CVD risk and cardiorespiratory fitness: The study population is all individuals from the IG, who participated in both baseline and re-examination, and all individuals from the CG, who participated in the examination.

Self-reported health and self-reported physical activity: The study population is all individuals from the IG, who completed both the baseline and the re-examination questionnaire, and all individuals from the CG, who completed the questionnaire.

Functional capacity: The study population is all individuals from IG, who participated in both baseline and re-examination, and all individuals from the CG, who participated in the examination.

5. Descriptive Analysis

To investigate participation patterns in the initial health check we analyze the binary participation status for the first invitation with respect to characteristics of the invited cohort (age, sex, socio-economic status, etc) in a logistic regression.

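### The objective is population-wide, but CVD risk, fitness, activity and self-rated health are estimated only in attenders, with no step to the invited population and no limit on the conclusion

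*SAP*

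**What the plan says.** Section 1 gives the trial's purpose as to "investigate the effectiveness on health outcomes of preventive health checks at a population level to all individuals aged 30 to 49 years". The aim in section 2 again describes the programme as population-based and applies this to CVD risk, physical activity, self-rated health and functional capacity.

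Section 4 defines who is analysed:

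- **CVD risk and fitness:** intervention group (IG) members seen both in year 2 and in year 5, and comparison group (CG) members seen in year 5.
- **Self-reported health and activity:** the same structure, with questionnaire completion in place of attendance.
- **Functional capacity:** also attenders, although these outcomes come from a national register.

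Section 4 also gives attendance: "A total of 55% of the invited population participated in the health check in year 1, 2012-2013". It adds: "We expect a similar proportion of the population will participate in the following years". It gives no rate of return among people who attended in year 2.

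In section 6, the first imputation step covers people who took part in the check they were randomised to. The propensity for re-examination is predicted for IG and CG members who attended their first check. Estimates are described as average treatment effects, and the section then states: "The treatment effects associated with participation in CHPP will be reported for each outcome measure with 95% confidence intervals". The whole invited population enters only for functional capacity, as a comparison that tests whether the weighting removes bias.

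**The concern.** The objective concerns what offering the check does for all residents in the age range. The planned estimates for four outcome areas concern what taking part does for people who come. These are different quantities. Better balance between the arms does not turn one into the other: even with perfect weighting, the estimate would still be an effect in attenders.

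At the expected attendance, about 45% of those randomised contribute nothing to these estimates. If the results are reported under the stated objective, the trial answers a narrower question than the one it poses, and the answer is too large for the municipality if non-attenders gain less than attenders.

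**Working it through.** **Inputs from the SAP.** 26,216 residents were randomised into five groups. The trial "included 10,505 individuals". First attendance is p = 0.55 (observed in year 1, similar expected later).

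**Inputs not in the SAP (assumptions).**

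- r: return rate among year-2 attenders
- f: effect in year-2 attenders who do not return, relative to two-time attenders
- g: effect in never-attenders, relative to two-time attenders

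**Step 1, the plan's own figure.** Two of five groups: 26,216 × 2/5 = 10,486, against 10,505 stated. The two agree within 0.2%. The SAP states no population-level effect or overstatement factor to reproduce.

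**Step 2, who is in the estimate.** Assuming equal groups, 10,505/2 ≈ 5,250 per group.

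- Expected first attenders: 5,252.5 × 0.55 ≈ 2,890 per group.
- IG two-time attenders if r = 0.55: 5,252.5 × 0.55 × 0.55 ≈ 1,590 (30% of those invited).
- IG two-time attenders if r = 0.80: 5,252.5 × 0.55 × 0.80 ≈ 2,310 (44%).

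**Step 3, dilution.** Population effect = effect in two-time attenders × [p·r + f·p·(1 − r) + g·(1 − p)]. The overstatement factor is 1/bracket.

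| Assumption | Bracket | Factor |
|---|---|---|
| f = 1, g = 0 (all first attenders share one effect), any r | 0.55 | 1.82 |
| f = 1, g = 0.25 | 0.55 + 0.45 × 0.25 = 0.6625 | 1.51 |
| f = 1, g = 0.5 | 0.55 + 0.45 × 0.5 = 0.775 | 1.29 |
| f = 0.5, g = 0, r = 0.55 | 0.3025 + 0.5 × 0.2475 = 0.426 | 2.35 |
| f = 0, g = 0, r = 0.90 | 0.495 | 2.02 |
| f = 0, g = 0, r = 0.80 | 0.44 | 2.27 |
| f = 0, g = 0, r = 0.60 | 0.33 | 3.03 |
| f = 0, g = 0, r = 0.55 | 0.3025 | 3.31 |

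Only the first row needs no number beyond the documented 55%, and it still needs g = 0 and f = 1. With g = 1 and f = 1 the factor is 1.0. The 1.3 to 3.3 range therefore covers the cases tried and is not a bound.

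**Step 4, what a larger factor requires.** With f = 0 and g = 0, a factor of 2 needs r = 0.5/0.55 = 0.91, and a factor of 3 needs r = 0.333/0.55 = 0.61.

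**Step 5, effect on the planned bias check.** Section 6 compares the propensity-weighted functional capacity estimate, made in attenders, with the estimate in everyone invited. Under the first row, and if the true effect is not zero, these differ by a factor of 1.82 even when the weighting works perfectly. The gap cannot be read as bias until the two targets are named.

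**The case against.** **The plan discloses the restriction.** Section 6 calls the result an effect of participation, section 4 sets out the populations outcome by outcome, and the SAP nowhere commits to presenting the attender estimate as the effect on the municipality. The introduction's population wording can also be read as describing the offer. This stands in part: nothing is hidden, and the harm depends on how the result is concluded. But one sentence in section 6 does not amend the objective, and the phrase average treatment effects is used without naming a population.

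**Population-wide evidence is planned elsewhere.** Section 6 uses the whole invited population for functional capacity, and section 8 lists a comparison with matched municipalities and an analysis of CVD and mortality. However, the first is only a check on the weighting, section 4 restricts functional capacity to attenders, and the section 8 analyses are to be described separately. None supplies an invited-population estimate for the four outcome areas here.

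**Non-attenders might be imputed.** Section 6 lists not having received the check among the reasons for missing outcomes. Its stated first step nevertheless limits imputation to participants, so the text does not support that reading.

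**Stronger readings that the document does not support.**

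- A reader might infer a two- to three-fold overstatement. That needs an unstated return rate of about 61% to 91%, and no benefit at all in people who had the year-2 check but did not return.
- A reader might take the weighting as aimed at likely returners. Section 6 does not say how the propensity enters the weights. Inverse weighting of IG returners would target all first attenders, while weighting the CG by the propensity would target returners.
- A reader might suppose that the cost-effectiveness work inherits the problem. Section 8 defers that work to a separate description, and nothing says it uses these estimates.

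**Conclusion.** The mismatch holds. The objective covers all residents aged 30 to 49, while CVD risk, fitness, self-reported activity and self-rated health are estimated among attenders or questionnaire completers only. The plan neither carries the estimates to the invited population nor confines the conclusion.

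The size that follows from the SAP's own attendance figure is about 1.8-fold, on two assumptions: no effect in never-attenders and one common effect in all first-round attenders. Across the other assumptions tried, it runs from about 1.3 to 3.3. All of these figures take the weighting as free of residual selection bias, which could push the estimate in either direction.

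This should be corrected, because it decides what the trial may conclude. It does not invalidate the attender analysis as an analysis of attenders.

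**What to change.** 1. In sections 2 and 6, name the target for these outcomes as the effect among attenders, and limit conclusions from them to attenders.
2. Beside each estimate, report an invited-population figure: the attender estimate multiplied by the observed first-attendance fraction of randomised IG members (about 0.55), under a stated assumption of no effect in never-attenders. Do not use the two-time-attender fraction as the main multiplier, since it treats a missing second measurement as missing benefit. At r = 0.60, if all year-2 attenders benefit equally, it would give 0.33 where 0.55 applies.
3. Add a sensitivity range that includes benefit limited to two-time attenders and a non-zero effect in non-attenders.
4. Reconcile sections 4 and 6 so that the register-based functional capacity outcomes are reported for everyone invited as a result in their own right, as well as serving the bias check.
5. Base population-level conclusions on items 2 to 4.

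The cost is SAP wording and a few multiplications per outcome, with no new data collection. The downside is a smaller population-level number that rests on stated assumptions.
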